13. DIRECT ACCESS TO SOURCE DATA/DOCUMENTS

13.1. Study Monitoring

Before an investigator can enter a subject into the study, Hepion (or representative) may visit the investigational study site to:

- Determine the adequacy of the facilities;
- Discuss with the investigator(s) and other personnel their responsibilities with regard to protocol adherence, and the responsibilities of Hepion (or representative). This will be documented in a Clinical Study Agreement between Hepion (or representative) and the investigator.

During the study, a monitor from Hepion (or representative) will have regular contacts with the investigational site, for the following:

- Provide information and support to the investigator(s);
- Confirm that facilities remain acceptable;
- Confirm that the investigational team is adhering to the protocol, that data are being accurately recorded in the CRF, and that investigational product accountability checks are being performed;
- Perform source data verification. This includes a comparison of the data in the CRF with the subject's medical records at the hospital or practice, and other records relevant to the study. This will require direct access to all original records for each subject (e.g., clinic charts);
- Record and report any protocol deviations not previously sent to Hepion (or representative);
- Confirm AEs and SAEs have been properly documented on CRFs and confirm any SAEs have been forwarded to Hepion (or representative) and those SAEs that met criteria for reporting have been forwarded to the IRB.

The monitor will be available between visits if the investigator(s) or other staff needs information or advice.

13.2. Audits and Inspections

Authorized Hepion employee (or representative), regulatory authority personal, or members of IEC or IRB may visit the site to perform audits or inspections including source data verification. The purpose of an audit or inspection is to systematically and independently examine all study-related activities and documents to determine whether these activities were conducted, and data were recorded, analyzed, and accurately reported according to the protocol, Good Clinical Practice, guidelines of the International Conference on Harmonization, and any applicable regulatory requirements. The investigator should contact Hepion immediately if contacted by a regulatory agency about an inspection.

13.3. Institutional Review Board

The investigator must obtain IRB approval for the investigation. Initial IRB approval, and all materials approved by the IRB for this study including the subject consent form and recruitment materials must be maintained by the investigator and made available for inspection.

14. QUALITY CONTROL AND QUALITY ASSURANCE

To ensure compliance with Good Clinical Practice and all applicable regulatory requirements, Hepion (or representative) may conduct a quality assurance audit. Please see Section [13.2](#) for more details regarding the audit process.

15. ETHICS

15.1. Ethics Review

The final study protocol, including the final version of the ICF, must be approved, or given a favorable opinion in writing by an IRB or IEC as appropriate. The investigator must submit written approval to Hepion (or representative) before he or she can enroll any subject into the study.

The investigator is responsible for informing the IRB or IEC of any amendment to the protocol in accordance with local requirements. In addition, the IRB or IEC must approve all advertising used to recruit subjects for the study. The protocol must be re-approved by the IRB or IEC upon receipt of amendments and annually, as local regulations require.

The investigator is also responsible for providing the IRB with reports of any reportable serious adverse drug reactions from any other study conducted with the investigational product. Hepion (or representative) will provide this information to the investigator.

Progress reports and notifications of serious adverse drug reactions will be provided to the IRB or IEC according to local regulations and guidelines.

15.2. Ethical Conduct of the Study

The study will be performed in accordance with ethical principles that have their origin in the Declaration of Helsinki and are consistent with International Conference on Harmonization /Good Clinical Practice, and applicable regulatory requirements.

15.3. Written Informed Consent

The investigator(s) at each center will ensure that the subject is given full and adequate oral and written information about the nature, purpose, possible risk and benefit of the study. Subjects must also be notified that they are free to discontinue from the study at any time. The subject should be given the opportunity to ask questions and allowed time to consider the information provided.

The subject's signed and dated informed consent must be obtained before conducting any study procedures.

The investigator(s) must maintain the original, signed ICF. A copy of the signed ICF must be given to the subject.

16. DATA HANDLING AND RECORDKEEPING

16.1. Inspection of Records

Hepion (or representative) will be allowed to conduct site visits to the investigation facilities for the purpose of monitoring any aspect of the study. The investigator agrees to allow the monitor to inspect the drug storage area, study drug stocks, drug accountability records, subject charts and study source documents, and other records relative to study conduct.

16.2. Retention of Records

The investigator must maintain all documentation relating to the study for a period of 2 years after the last marketing application approval, or if not approved 2 years following the discontinuance of the test article for investigation. If it becomes necessary for Hepion (or representative) or the Regulatory Authority to review any documentation relating to the study, the investigator must permit access to such records.

1. INTRODUCTION

This statistical analysis plan (SAP) is prepared in conjunction with the Hepion Pharmaceuticals, Inc.'s protocol number HEPA-CRV431-201 titled, "AMBITION: A Phase 2A, Multi-Center, Single-Blind, Placebo-Controlled Study to Evaluate the Safety and Tolerability of CRV431 Dosed Once Daily in NASH induced F2 and F3 Subjects" .

The primary purpose of this study is to evaluate the safety and tolerability and pharmacokinetics (PK) of CRV431 in subjects with presumed nonalcoholic steatohepatitis (NASH) F2/F3 fibrosis.

This SAP provides detailed description of the statistical methods specified in the protocol. An interim analysis will be performed when at least six (6) subjects in Cohort A (CRV431 75 mg) and at least three (3) subjects in Cohort B (matching placebo) have reached 28 days of dosing. The DSMB will also review the Day 28 safety data from the remaining subjects to confirm there are no changes to the prior safety assessment. The final planned analyses will be performed after database lock.

2. OBJECTIVES AND ENDPOINTS

2.1 Objectives

2.1.1 Primary Objective

- To evaluate the safety and tolerability of once daily (QD) 75 mg and 225 mg doses of CRV431 in presumed NASH fibrosis stage 2 (F2)/fibrosis stage 3 (F3) subjects compared to placebo control over 28 days of dosing
- To evaluate the pharmacokinetics (PK) of a QD dose of CRV431, its major metabolites and fraction unbound in presumed NASH F2/F3 subjects over 28 days of dosing.

2.1.2 Secondary Objectives

- To evaluate non-invasively the antifibrotic activity of a QD dose of CRV431, as measured by quantification of selected biomarkers of fibrosis, in presumed NASH F2/F3 subjects over 28 days of dosing.

2.1.3 Exploratory Objectives

- [REDACTED]

Metalloelastase], MMP-13 [Collagenase 3]) and tissue inhibitor of metalloproteinase

[REDACTED]

2.2 Endpoints

2.2.1 Study Endpoints

2.2.1.1 Safety Endpoints

Safety and tolerability parameters, including AEs, SAEs, AEs of special interest, physical examinations including weight and height, concomitant medications, laboratory assessments including blood chemistry, hematology and coagulation, urinalysis, pregnancy screening, ECG, and vital sign assessments, will be determined.

2.2.1.2 Pharmacokinetic Endpoints

The PK parameters for CRV431 in whole blood will be determined in subjects in fasted state. A list of PK parameters is shown in Table 5 in the protocol.

On an exploratory basis, concentration-effect relationships will be explored between CRV431 whole blood concentrations and all biomarkers measured. Subject demographics and clinical laboratory data will be evaluated as potential covariates in PK/PD model using non-linear mixed effect modeling with direct and indirect models.

2.2.2 Exploratory Endpoints

Assessments of biomarkers of collagen, lipidomics, and RNA sequencing.

3. INVESTIGATIONAL PLAN

3.1 Study Design

This is a randomized, single-blind, placebo-controlled, QD dose study of CR431 in presumed NASH F2/F3 subjects. This study will consist of 3 phases: (i) Screening and Randomization; (ii) treatment; and (iii) follow up.

3.1.1 Screening and Randomization Period

Screening visits will be conducted within 30 days prior to study Day 1.

Upon determination that a subject meets all eligibility criteria, the subject will be randomized on Study Day -1 to receive either CRV431 or matching placebo in a 2:1 subject ratio (12 CRV431 75mg to 6 matching placebo and 12 CRV431 225mg to 6 matching placebo).

Table 1: Study Design

Cohort*	Fibrosis Stage	N	Day 1 – 28, fasted oral dosing	Day 29 - 42
A	F2/F3	12	CRV431 75 mg	Observation/Follow up
B		6	Placebo ^a	
C		12	CRV431 225 mg	
D		6	Placebo ^b	
*Randomized assignment; 2:1 – CRV431: Placebo				
^a Matching Placebo for Cohort A - 75 mg dose.				
^b Matching Placebo for Cohort C - 225 mg dose.				

3.1.2 Treatment Period

Subjects will receive treatment with CRV431 or placebo from Day 1 to Day 28.

3.1.3 Follow Up Period

After completion of the treatment period, the subjects will be monitored for additional 14 days.

3.2 Treatment

Subjects in Cohort A will receive CRV431 75 mg (1 x 75 mg softgel capsule) QD and subjects in Cohort B will receive the matching placebo (1 x placebo softgel capsule) for Cohort A.

Subjects in Cohort C will receive CRV431 225 mg (3 x 75 mg softgel capsules) QD and subjects in Cohort D will receive the matching placebo (3 x placebo softgel capsules) for Cohort C.

3.2.1 Treatment Administration

Subjects will take study drug on the morning of each dosing day, with approximately 240 mL of water. On Day 1 and Day 28, subjects will fast overnight for at least 8 hours, will take CRV431 or matching placebo and will fast for an additional 2 hours after treatment administration. On subsequent days, subject will fast overnight for at least 8 hours, will take CRV431 or matching placebo and will fast for an additional 30 minutes after treatment administration.

3.2.2 Treatment Compliance

While in the Clinical Research Unit, study treatment will be administered under the supervision of site personnel. Compliance during the non-study visit days will be assessed by subject report

and pill count. A qualified designee will be responsible for monitoring the administration of the timed oral doses on study visit days.

4. GENERAL CONSIDERATIONS FOR DATA ANALYSIS

Unless otherwise specified, continuous variables will be summarized by presenting the number of non-missing observations, mean, standard deviation, median, minimum, and maximum. Categorical variables will be summarized by presenting the number of subjects and percentages for each category.

All mean and median values will be formatted to one more decimal place than the measured value. Standard deviation values will be formatted to two more decimal places than the measured value. Minimum and maximum will be formatted to the same number of decimal places as the measured value.

Analyses will be performed using SAS for Windows statistical software, version 9.4 or higher (SAS, Cary, NC), except where other software may be deemed more appropriate.

[REDACTED]

4.1 Data Quality Assurance

Once all the source verification is complete, all queries are resolved, and the database has been updated appropriately, the database will be locked and made available to CTI Biostatistics for final analysis.

[REDACTED]

All SAS programs used to create analysis data sets, tables, listings, and figures are double programmed. The SAS outputs will be compared, and the programs will be updated until the outputs match.

4.2 Analysis Sets

4.2.1 Pharmacokinetic Set

The Pharmacokinetic Set is defined as all subjects who comply sufficiently with the protocol and

display an evaluable PK profile (e.g., exposure to treatment, availability of measurements and absence of major protocol violations). Samples from all subjects will be assayed even if the subjects do not complete the study.

4.2.2 Safety Set

The Safety Set is defined as all subjects who received the study drug or placebo.

All safety analyses will be performed using the Safety Set.

4.3 Assessment Windows

For the purpose of listing and summarizing data, the time-in-study for each subject observation will be defined using study days as defined in the Schedule of Events (Appendix A). No analysis windows are planned for the study regarding data collected outside the protocol specified windows. All data will be included in the analysis based on the visit as it is recorded in the database.

4.4 Handling of Dropouts or Missing Data

Missing data will remain missing. No imputation of missing data will be performed.

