6.3. Exploratory Objectives

- To generate exploratory data regarding the antifibrotic activity of a QD dose of CRV431 over 28 days of dosing by performing hepatic evaluations via laboratory assessments of biomarkers [REDACTED]

- [REDACTED]
- [REDACTED]
- [REDACTED]
- [REDACTED]
- [REDACTED]

- ALT and/or AST decrease from baseline.

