A decision to discontinue or temporarily interrupt the study drug for a subject will be considered based on following criteria:

- If ALT/AST baseline measurements (BLM) are <2 x ULN, discontinue if ALT or AST increases to >5 x BLM;
- If ALT/AST BLM \geq 2 x ULN but <5 x ULN, discontinue if ALT or AST increases to 3 x BLM;
- If ALT/AST BLM \geq 5 x ULN, discontinue if ALT or AST increases to >2 x BLM AND the increase is accompanied by a concomitant increase in TBL to >2 x BLM OR the International Normalized Ratio (INR) concomitantly increases by >0.2;
- Any subjects with signs and symptoms of fatigue, nausea, vomiting, right upper quadrant pain or tenderness, fever, and/or rash, accompanied by a >5% increase in eosinophils;
- Subjects who miss more than 2 consecutive QD doses of study drug. Subjects may be replaced unless a stopping rule precludes replacement.

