7.3 Clinical Laboratory Assessments

Hematology, Coagulation, Blood Chemistry and Urinalysis data will be summarized by treatment group and visit. All clinical laboratory data will be converted to International System of Units (SI). Both raw and change from baseline values will be summarized by presenting the descriptive statistics by treatment group and visit.

Central and local drug and alcohol test results and pregnancy tests results will be listed.

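### A subject who leaves the study early for an ALT or AST rise drops out of the Day 28 change-from-baseline summary, and no all-dosed summary is planned to show the effect

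*Combined protocol and SAP*

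**What the plan says.** Four SAP rules act together.

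- **SAP 4.4** (dropouts and missing data): "Missing data will remain missing. No imputation of missing data will be performed".
- **SAP 4.3** (assessment windows) plans no analysis windows: "All data will be included in the analysis based on the visit as it is recorded in the database".
- **SAP 7.3** (laboratory): "Both raw and change from baseline values will be summarized by presenting the descriptive statistics by treatment group and visit".
- **SAP 4** (general) sets the statistics: "continuous variables will be summarized by presenting the number of non-missing observations, mean, standard deviation, median, minimum, and maximum".

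The protocol uses the aminotransferases in two ways. Section 6.3 lists as an exploratory objective "ALT and/or AST decrease from baseline", with no visit or estimator named. Sections 7.7 and 8.3.1 use rises in the same enzymes, and laboratory abnormalities generally, to stop drug or end participation.

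Protocol 8.3.1 requires a subject to leave the study for, among other reasons, a hepatic event judged to be DILI and drug-related, or a related Grade 3 or 4 laboratory abnormality. Such a subject has an Early Termination visit, at which Table 3 schedules blood chemistry. Safety follow-up continues, but the text does not require a Day 28 chemistry sample. Protocol 8.4 allows replacement on the same treatment assignment.

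**The concern.** Whether a Day 28 value exists depends on the quantity being averaged. A subject removed for a rise has the last value filed under Early Termination, and nothing fills the Day 28 cell. The Day 28 mean change is then taken over those who did not rise enough to be removed. If the subject is replaced, the Day 28 count can return to twelve and the table gives no sign of the loss.

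Two readings are at stake. One is any statement that ALT or AST fell, which would feed the Phase 2B planning named in the synopsis. The other is the laboratory safety table, which serves a primary objective. Protocol 12.3.5 promises a laboratory shift table, but neither SAP 7.3 nor the table list in SAP Appendix B shows one, and no table of maximum post-baseline values is listed.

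**Working it through.** **Plan's own figure.** There is none to reproduce. The documents give no expected ALT/AST change, SD, dropout rate or stopping rate, and the sample size is stated not to rest on statistical requirements.

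**Inputs from the documents.** 12 active and 6 placebo subjects per dose level (protocol 7.2). Multiples of baseline from protocol 7.7.1: 3 times baseline (DILI is described there as aminotransferases above 3 x ULN or 3 x baseline) and 5 times baseline ("If ALT/AST baseline measurements (BLM) are <2 x ULN, discontinue if ALT or AST increases to >5 x BLM"). They are used here only to size a rise.

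**Inputs assumed.** Changes in the other subjects, the baseline of the subject who leaves, and all stopping rates.

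**Within one active arm.** Eleven subjects change by -5 U/L. One with baseline b = 40 U/L leaves at m times baseline, a change of (m - 1) x b.

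- Day 28 mean as planned: 11 x (-5) / 11 = -5.0 U/L.
- All dosed, m = 3: (11 x (-5) + 2 x 40) / 12 = 25 / 12 = +2.1 U/L.
- All dosed, m = 5: (11 x (-5) + 4 x 40) / 12 = 105 / 12 = +8.8 U/L.
- With a replacement also at -5 (12 at Day 28, 13 dosed): (-60 + 80) / 13 = +1.5 and (-60 + 160) / 13 = +7.7 U/L, against -5.0 on a full count of 12.

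**If the value has fallen by the last sample.** At 2 times baseline: (-55 + 40) / 12 = -1.3 U/L. Back at baseline: -55 / 12 = -4.6 U/L. The sign does not reverse in either case.

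**Break-even, in percent of baseline.** One subject at m times baseline offsets any mean decrease in the other eleven smaller than (m - 1) x 100 / 11: 36.4% for m = 5 and 18.2% for m = 3. With a replacement the divisor is 12, giving 33.3% and 16.7%.

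**Against placebo.** Assume others change by -10% on active and 0% on placebo, and those who leave are at 5 times baseline (+400%). The Day 28 difference is always -10 points.

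| Exits, active v placebo | All-dosed active | All-dosed placebo | All-dosed difference | Day 28 minus all-dosed |
|---|---|---|---|---|
| 1/12 v 0/6 | +24.2 | 0 | +24.2 | -34.2 (favours drug) |
| 2/12 v 1/6 | +58.3 | +66.7 | -8.3 | -1.7 (nearly cancels) |
| 1/12 v 1/6 | +24.2 | +66.7 | -42.5 | +32.5 (against drug) |

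**Median.** In the U/L example the median is -5 with or without the twelfth subject. In a simulation with mean -10 and assumed SD 20 points, adding one subject at +400 moved the median by about 2 points and the mean by about 34.

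**How often this arises.** The chance of at least one such exit among 12 active subjects is 1 - (1 - p)^12: 21.5%, 46.0% and 71.8% for assumed p of 2%, 5% and 10%.

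**The case against.** **Stopping drug is not leaving the study.** A reader might infer that anyone meeting the ALT/AST multiples in protocol 7.7.1 goes to Early Termination. The text does not say so. Those multiples lead to discontinuation or temporary interruption of drug being considered, and such a subject can still attend Day 28. This stands, so the point rests on the mandatory exits in 8.3.1.

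**The analysis of the objective is not visible.** SAP 6.3 is redacted, and the visible exploratory endpoint text ("Assessments of biomarkers of collagen, lipidomics, and RNA sequencing") does not name ALT or AST. That the decrease will be judged on a Day 28 mean is inferred from SAP 7.3. This stands too, although SAP 4.3 and 4.4 are general rules and the laboratory table is affected in any case.

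**The direction is not fixed.** A reader might infer that the plan biases the result in the drug's favour, or that a more hepatotoxic arm always looks better. Neither is supported. Rises that do not lead to exit, or that first appear at Day 28, stay in and worsen the mean, and the placebo comparison can go either way. Relatedness is judged by an unblinded investigator and sponsor (protocol 7.3.3), so proportionally more exits on active are plausible, but the documents do not establish them.

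**The subjects are not hidden.** They remain in the Safety Set, at earlier visits, in adverse event and withdrawal tables, in listings, and possibly in an Early Termination row. Medians and numbers observed are already planned. A confirmed related DILI pauses dosing for DSMB review (protocol 7.7.2). This limits the harm, but none of it gives an ALT/AST change over everyone dosed.

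**Conclusion.** The mechanism follows from the visible text: an exit before Day 28 for an ALT/AST rise removes that subject from the Day 28 summary, and replacement can restore the count. The within-arm Day 28 mean would then be more favourable than the all-dosed mean. In the illustration the gap is 7.1 U/L (3 times baseline) or 13.8 U/L (5 times), enough to reverse the sign of a -5.0 U/L mean if the last value is still near its peak.

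This is conditional. It needs at least one such exit, and no rate is given. Only the within-arm direction is supported. The size rests on assumed changes in the other subjects and on how far the value has fallen by the last sample.

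A reader might go further and want a carried-forward or Early Termination value to replace Day 28 as the sole basis for the ALT/AST objective. That is debatable, because an Early Termination sample may be off drug and recovering. The objective is exploratory and the visible laboratory analysis is descriptive, so the consequence is for interpretation and Phase 2B planning. It is a cheap improvement worth making.

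**What to change.** In SAP 7.3 and Appendix B, keep the by-visit rows and add three items for ALT and AST, by arm, in all dosed subjects including any who were replaced:

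1. Change from baseline to the last on-treatment value. State the interval after the last dose that still counts as on treatment, and show off-drug Early Termination values separately.
2. The maximum post-baseline value, including repeat and unscheduled samples.
3. The number who stopped drug and the number who left the study for ALT/AST.

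State that any claim of an ALT/AST decrease is to be read alongside these rows.

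The cost is a few derived rows from data already collected. The small downside is that, for the few who stop, an early last value stands beside other subjects' Day 28 values.

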4.5 Multiple Comparisons

There are no multiple comparisons.

